3.2 Secondary Endpoints

The following secondary endpoints will be evaluated using descriptive statistics to provide further information related to the safety and performance of the Pristine™ Long-Term Hemodialysis Catheter. All secondary endpoints will be summarized with descriptive statistics.

- *Rate of freedom from catheter-related bloodstream infection (CRBSI)*, defined by 2019 KDOQI Guidelines for CRBSI through 1-month, 3-months, 6-months, and 12 months post-index procedure.

- *Rate of freedom from Device and/or Procedure-related adverse events*, at 1-month, 3-months, 6-months, and 12 months post-index procedure.
- *Rate of Technical Success*, defined as the successful placement of the Pristine™ Long-Term Hemodialysis Catheter, as assessed by the Investigator during the Index Procedure.
- *Overall Participant Survival Rate* at 1-month, 3-months, 6-months, and 12 months post-index procedure, defined as the proportion of participants that have not died from any catheter related complication.
- *Overall Catheter Survival Rate* at 1-month, 3-months, 6-months, and 12 months post-index procedure, defined as the proportion of Pristine™ Catheters that have not been removed for any cause.
- *Overall Patency Rate*, at 1-month, 3-month, 6-months, and 12-months post-index procedure, defined as the Pristine™ catheter having the ability to achieve a mean dialysis blood flow of $\geq 300\text{mL/min}$ without need for additional interventions.^{5,6}

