Participants were followed for 6 months post-catheter implantation at four sites that were affiliated with the placement institution. All catheters (n=44) were patent at 30 days post implantation. Primary patency at 60- and 180- days post procedure was 100.0% and 90.9%, respectively. The following adverse events (AE) were reported in accordance with MedDRA v. 22.1. There were 9 infections, 6 of which were reported as device-related and 3 (2 pneumonia and 1 abdominal abscess) were reported as not related to the study device. There were 2 cardiac disorders and 2 vascular disorders, none of which were reported as device related. There were 6 general disorder and access site conditions, 2 of which were reported as device related. There were 9 deaths reported in the study, none of which were reported as related to the device or procedure.³

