7.5 Participant Investigation Completion and Premature Discontinuation

Following the index procedure, every participant into whom the Pristine™ Catheter was placed should remain in the study until completion of the required follow-up period or until day of remove of the Pristine™ Catheter. The follow-up period for this clinical investigation is 12 months (365 ± 30 days) for participants who had the Pristine™ Catheter successfully placed. An enrolled participant is considered to have completed the study if the participant has completed the formal follow-up period associated with this clinical investigation through the 12-Month follow-up as described in the Schedule of Activities (Section 1.3).

Upon investigation completion or premature discontinuation (in the situations where applicable), the participant's continued care should be administered per SOC at the discretion of the PI and / or their primary care physician.

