8 PARTICIPANT DISCONTINUATION/WITHDRAWAL

8.1 Discontinuation/Withdrawal

- A participant may withdraw from the study at any time at his/her own request (Withdrawal of Consent) or may be withdrawn at any time at the discretion of the investigator (Investigator's Decision) or sponsor (Sponsor's Decision) for safety, behavioral, compliance, or administrative reasons.
- Once a participant discontinues from the study, no further data will be collected.
- If the participant withdraws consent for disclosure of future information, the sponsor may retain and continue to use any data collected before such a withdrawal of consent.
- If a participant withdraws from the study, the reason for withdrawal must be documented.

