### **5.3.4 Overall Participant Survival Rate at 1-month, 3-months, 6-months, and 12-months post-index procedure, defined as the proportion of participants that have not died from any catheter related complication.**

## Binary Analysis

Subject will be considered as a failure of the endpoint for a given visit if the subject has experienced the death due to a catheter-related complication prior to the upper limit of visit window for the visit:

- **Disposition-End of Study CRF Page:** Date of Death <= upper limit of the visit window  
**AND AE CRF Page:** Relationship to Device: Is 'Related' or 'Likely Related' AND Does the Event Meet the Definition of an SAE: Is Yes AND Results in Death: Is Yes and subject will be considered as a failure at the Death date

If the subject has not become failure and experience one of the following events prior to the lower limit of visit window, then subject will be considered as non-evaluable at the earliest occurrence of following event dates.

- Catheter has been removed due to Kidney Transplant, Transferred to AVG/AVF, Peritoneal Dialysis, Withdrawal of Care, or Other reasons
  - *Hemodialysis Catheter Re-Interventions CRF page: Catheter removal Equals Yes AND Reason for catheter removal Equals: Kidney Transplant, Transferred to AVG/AVF, Peritoneal Dialysis, Withdrawal of Care, or Other*

OR

- Subject has discontinued from the study.

If the subject has experienced any of the above non-evaluable events prior to the lower limit of visit window subject will be counted as a non-evaluable for a given visit. Else subject will be considered as a success of the endpoint for a given visit.

The overall participant survival rate will be reported with 95% confidence interval from the exact binomial method. The analysis will be performed on the mITT population through 1-month, 3-months, 6-months, and 12-months.

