## KM Analysis

KM analysis will be used to estimate the time from the date of index procedure to the date of death and to determine the overall participant survival rate at 1-, 3-, 6-, and 12-months. Catheter-related death is considered as the event.

Subjects that have not reached catheter-related death (event) will be censored or considered event free as described below.

- If the subject has experienced following events, subject will be censored at the earliest date of those events.
  - Catheter has been removed due to Kidney Transplant, Transferred to AVG/AVF, Peritoneal Dialysis, Withdrawal of Care, or Other reasons
  - Subject has discontinued from the study.

Note: How to assess the above events has been described in **Error! Reference source not found.**the Binary Analysis section.

- All the other subjects will be considered event free and will be censored on visit day (visit day can vary from lower limit to upper limit of visit window).

This endpoint will be evaluated on the mITT population through 1-month, 3-months, 6-months, and 12-months.

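### 'Overall Participant Survival Rate' counts only device-attributed deaths, so it can read near 100% whatever the all-cause mortality, and no all-cause survival estimate is planned

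*Protocol*

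**What the plan says.** Protocol 3.2 (Secondary Endpoints) and SAP 2.7.2 give the 'Overall Participant Survival Rate' at 1, 3, 6 and 12 months, "defined as the proportion of participants that have not died from any catheter related complication". It is a descriptive endpoint with no hypothesis test.

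SAP 5.3.4 turns the definition into rules for the mITT population:

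- **Failure (binary).** There must be a date of death on or before the upper window limit, and an AE record that is device 'Related' or 'Likely Related' and meets "Does the Event Meet the Definition of an SAE: Is Yes AND Results in Death: Is Yes".
- **Non-evaluable (binary).** A non-failure is non-evaluable if, before the lower window limit, the catheter is removed for a listed reason or "Subject has discontinued from the study".
- **Success (binary).** Everyone else is a success. "The overall participant survival rate will be reported with 95% confidence interval from the exact binomial method".
- **KM.** "Catheter-related death is considered as the event". Discontinuation is a censoring event, and all remaining subjects are censored event-free at the visit day.

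SAP 5.3.4 does not itself say how a death from another cause is classed. Protocol Appendix A does, under 'Access Censoring Events', where participant death is one of the forms of premature discontinuation.

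On the earlier feasibility study, Protocol 2.1 reports: "There were 9 deaths reported in the study, none of which were reported as related to the device or procedure".

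**The concern.** The label and the content differ. 'Overall survival' is ordinarily read as survival from death of any cause. The neighbouring item in the same protocol list, overall catheter survival, is defined there by removal for any cause, so a reader has reason to take 'overall' the same way for participants. What is measured is freedom from a death that has been attributed to the device.

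Protocol section 3 says the study information is meant for the device labelling. A survival rate close to 100% under this name could stand there beside substantial mortality. It would depend on how relatedness was rated, and no survival estimate that is free of that rating is planned to set beside it.

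**Working it through.** **1. Where an unrelated death goes**

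| Timing of death | Binary analysis | KM analysis |
|---|---|---|
| Before the lower window limit | Non-evaluable: leaves numerator and denominator | Censored |
| On or after the lower window limit | Success: stays in both | Censored |

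No cell is a failure. The result does not hinge on the Appendix A link. If a death were not treated as a discontinuation, the subject would fall into the residual category, which is a success in the binary analysis and event-free in KM.

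**2. Feasibility figures (Protocol 2.1)**

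Inputs: 45 received the catheter, follow-up was 6 months, and there were 9 deaths, of which 0 were judged related.

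- Mortality: 9/45 = 20.0%. With the n = 44 given for 30-day patency it is 9/44 = 20.5%.
- Crude all-cause survival: (45 − 9)/45 = 36/45 = 80.0%, Clopper-Pearson 95% CI 65.4% to 90.4%.
- SAP binary rule: let k be the number of the 9 deaths before the lower window limit. The rate is (45 − k)/(45 − k). With k = 9 it is 36/36 = 100% (95% CI 90.3% to 100%). With k = 0 it is 45/45 = 100% (95% CI 92.1% to 100%). Death dates are not given, so k is unknown, but the rate is 100% for every k. This assumes no other exits or removals among the survivors. Any such exits would shrink the denominator and leave the rate unchanged.
- SAP KM rule: the estimate is the product of (1 − d/n) over event times, where d counts related deaths only. With no related deaths every factor is 1, so KM = 100%.

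**3. Dependence on attribution at the planned size**

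Assume 142 treated participants and 28 deaths (0.20 × 142 = 28.4). The 20% is borrowed for illustration. All-cause survival is then 114/142 = 80.3% (95% CI 72.8% to 86.5%). Let r of the 28 deaths be judged related. If all unrelated deaths are non-evaluable, the SAP rate is 114/(114 + r). If all unrelated deaths are successes, it is (142 − r)/142.

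| r | 114/(114 + r) | (142 − r)/142 |
|---|---|---|
| 0 | 100% (95% CI 96.8% to 100%) | 100% |
| 3 | 97.4% | 97.9% |
| 6 | 95.0% | 95.8% |
| 14 | 89.1% | 90.1% |

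For KM, with proportional cause-specific hazards and a share f of deaths judged related, the estimate is 0.80^f. That is 97.8% at f = 0.10 and 95.6% at f = 0.20.

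**The case against.** The case for leaving the endpoint alone has several parts.

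- **The definition is open.** It is worded consistently in Protocol 3.2, SAP 2.7.2 and SAP 5.3.4, and cause-specific death is a legitimate device-safety measure. This stands as a defence of the measure. It does not defend the name.
- **Deaths will be visible.** A reader might infer that the report would contain no all-cause mortality information. The documents do not support that. SAP 6.1 tabulates discontinuations by reason, SAP 7 tabulates and lists SAEs, and Protocol 9.4 (Table 4) requires all-cause deaths to be reported to the sponsor. What is missing is a survival estimate over time. A count does not supply one.
- **Not every unrelated death is dropped.** A reader might infer that all are removed from the denominator. Under SAP 5.3.4 those on or after the lower window limit remain as successes, so 36/36 is only one end of a range running to 45/45.
- **The 20% does not transfer.** The feasibility study was at a single site in the Dominican Republic and included acute renal failure. This trial enrols ESRD at US sites and excludes participants whose life expectancy is too short for follow-up. This stands: the figure shows how the rule behaves and does not forecast mortality here.
- **Deaths after catheter removal.** Protocol 7.5 says participants "should remain in the study until completion of the required follow-up period or until day of remove of the Pristine™ Catheter", and Protocol 8.1 says "Once a participant discontinues from the study, no further data will be collected". A reader might infer that a death from infection soon after removal would be missed. That is not established. Protocol 9.1.1 requires an AE to be followed until it resolves, stabilises or is no longer clinically significant. Removal for infection or dysfunction is also not among the removal reasons that make a subject non-evaluable or censored in SAP 5.3.4. The three protocol sections need reconciling, but that is a separate matter.

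**Conclusion.** The concern holds. The endpoint named 'Overall Participant Survival Rate' is freedom from device-attributed death. Deaths from other causes can never lower it as failures, and some are counted as successes. On the feasibility figures the gap is 20 percentage points: 100% under the SAP rule against 80.0% crude all-cause survival. The size in this trial depends on two unknowns, the mortality and the share of deaths rated 'Related' or 'Likely Related'. A rate near 100% requires that share to be small. If half of 28 assumed deaths were rated related, the rate would be about 89% to 90%.

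The endpoint is secondary and descriptive, so the primary test is unaffected. The risk is a misleading mortality statement in results meant for labelling. It should be corrected before reporting.

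**What to change.** 1. Rename the present endpoint 'Freedom from catheter-related death' in Protocol 3.2 and in SAP 2.7.2 and 5.3.4. State that a death from another cause is not a success. Treat such deaths as a competing event and report catheter-related death by cumulative incidence.
2. Report 'Overall Participant Survival' as all-cause KM at 1, 3, 6 and 12 months in the mITT population. Every on-study death is an event, dated from the Date of Death on the Disposition-End of Study CRF, with censoring at study exit for reasons other than death.

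The cost is one extra table, a wording change in both documents and a less favourable survival figure. No new data are needed for deaths on study. If participation does end at catheter removal, the all-cause curve will be censored there, and the report should say so. Added vital-status calls are not proposed, because they would presuppose contacts that Protocol 7.5 and 8.1 may not provide. Those sections and 9.1.1 should be reconciled separately.

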3.3 Exploratory Endpoints

The following endpoints may be evaluated in an exploratory fashion. Data will be collected throughout the course of the investigation in support of this endpoint.

- *Kit Component Safety and Performance*, defined as the overall rate of the catheter's procedure kit component complications from time of procedure to discharge.

4 STUDY DESIGN

4.1 Overall Design

This is a prospective, multi-center, post market, single-arm study designed to assess the safety and performance of the Pristine™ Long-Term Hemodialysis Catheter. The primary objective of this study is to assess the overall complication rate of the Pristine™ Catheter against an overall hemodialysis catheter complication rate derived from clinical literature.

A total of 142 patients will be enrolled and have the Pristine™ Long-Term Hemodialysis Catheter placed. Under the current enrollment assumptions, up to 15 investigational sites in the United States (US) will participate. The study will be enrolling male or non-pregnant female participants ≥ 18 years of age meeting study inclusion/exclusion and labeled indication for hemodialysis for adequate completion of study procedures and collection of data. Eligible participants will have End Stage Renal Disease requiring hemodialysis through a tunneled dialysis catheter. Follow-up for all enrolled participants will be performed at 1-month, 3-months, 6-months, and 12-months post-Index Procedure. No site will be allowed to enroll more than 20% of the overall number of participants to ensure a reasonably well-balanced, multi-center study.

For this study, we have a combined Safety and Performance endpoint derived from the Dialysis Outcomes and Practice Patterns Study (DOPPS) data.⁴ Our combined Primary Endpoint will be overall complications including non-infectious and infectious at 3 months.

4.2 Scientific Rationale for Study Design

The combined safety and performance primary endpoint is compared to a performance goal of 31.5 complications per 1000 catheter days derived from the Dialysis Outcomes and Practice Patterns Study (DOPPS).⁵ The DOPPS data was chosen due to it's significant sample size of tunneled catheters (n=4207) and it's clear definition of non-infectious and infectious complications. DOPPS I-III enrolled 27, 129 participants that provided access data. DOPPS I enrolled within France, Germany, Italy, Japan, Spain, the United Kingdom, and the United States. DOPPS II and DOPPS III enrolled in Australia, Belgium, Canada, New Zealand, and Sweden.⁵ There have been few hemodialysis catheter studies performed in the last 10 years with many lacking sufficient sample size for statistically powered endpoints. The hemodialysis catheter studies that report 'complication' rates or infection rates have a significant variance in definitions. The KDOQI guidelines have stated a need for consistent definitions and outcomes between tunneled catheter studies.⁶ DOPPS is a globally renowned study providing clinically meaningful definitions with a significant sample size not seen in other studies.

The primary endpoint for this study is a combined complication rate of non-infectious and infectious complications. Non-infectious complications are defined as, complications due to any noninfectious cause (thrombosis of the access, fibrin material within or around a catheter, catheter migration, central vein stenosis or thrombosis) requiring a revision procedure to maintain patency or improve access performance (i.e., thrombolysis, angioplasty, or surgical correction) in an inpatient or outpatient setting or removal or abandonment with creation of a new access that was not due to an access-related infection). This definition of non-infectious provides the clinically relevant point of re-intervention. Thrombosis, fibrin material, and catheter migration are all common events for tunneled catheters. When these events start to disrupt dialysis treatment, they require re-intervention thus putting more burden on the patient and healthcare system. The other part is infectious complications defined as, complications due to any documented diagnosis of access infection requiring medical intervention (managed in an outpatient or inpatient setting) or sepsis as diagnosis in the hospitalization file whether access related or not. Infection rate for catheters is arguably the most crucial reported value being the main cause of catheter related deaths. The infectious complications defined include exit site infections and all blood stream infections causing sepsis.

Showing a statistically significant difference by our powered primary endpoint against the performance goal will attest to the performance, safety, and clinical benefits of the Pristine™ Catheter.

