10.2 Sample Size Considerations

The primary objective of the study is to show the overall complication rate for Pristine is non-inferior to the performance goal at 3 months. If successful, the next step is to show superiority of Pristine at 3 months.

Based on hypothesis test of Non-inferiority

- Assumptions:
 - The complication rate of our performance goal is estimated at 31.5 events per 1000 patient days with a 90 days follow-up based on DOPPS study data. The complication rate for Pristine is expected to be similar.
 - The performance goal is set at 36.5 events per 1000 days using a 5 events per 1000 days non-inferiority margin;
 - The attrition through 90 days is assumed to be 15%
 - The Type 1 error is 0.025 (one-sided).

- The Type 2 error is 0.2.
- Sample Size:
 - Total required exposure is 12765 patient days which translates to 142 participants with average exposure of 90 days (PASS 2019).

Based on hypothesis test of Superiority

- Assumptions:
 - The complication rate of our performance goal is estimated at 31.5 events per 1000 patient days with a 90 days follow-up based on literature review, which is set as the performance goal.
 - The complication rate for the Pristine™ Catheter is assumed to be 26.5 events per 1000 patient days.
 - The attrition through 90 days is assumed to be 15%
 - The Type 1 error is 0.025 (one-sided).
- Sample Size:
 - Total exposure of 12765 patient days (which translates to 142 participants with average exposure of 90 days) will provide 85% power of the test (PASS 2019).

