10.5 Primary Endpoint

The combined primary endpoint is the overall rate of infectious complications and non-infectious complications requiring revision to maintain patency and improve access performance at 3 months. Based on the DOPPS study data, competitor control devices had an average incidence rate of 31.5 complications per 1000 patient days. To show non-inferiority of the Pristine™ Catheter, a 5 complications per 1000 patient days non-inferiority margin is used to establish a performance goal (PG) of 36.5 events per 1000 patient days.

The analysis of the primary endpoint will be based on the following test of Poisson rate:

H₀: The complication rate through 3 month is greater than or equal to 36.5 events per 1000 patients days at 3 months.

H₁: The complication rate through 3 month is less than 36.5 events per 1000 patient days at 3 months.

That is:

$$\mathbf{H_0: \lambda \geq \lambda_0}$$

$$\mathbf{H_1: \lambda < \lambda_0}$$

Where λ_0 is the PG of 36.5 events per 1000 patient days.

A one-sided p-value will be derived based on an Poisson distribution. The Pristine™ Catheter will be considered to have achieved the primary endpoint objective if the one-sided p-value is less than 0.025.

Conditioned on the success of the above test, a superiority test will be conducted to show that the Pristine™ Catheter is superior to the performance goal. The above test will be repeated with a PG of 31.5 events per 1000 patient days.

The analyses of the primary endpoint will be based on the ITT population and repeated with per-protocol population as sensitivity analyses.

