### 5.2.2 Hypothesis Testing

The primary endpoint is the overall rate of infectious complications and noninfectious complications requiring revision to maintain patency and improve access performance at 3 months. Based on the DOPPS study data, competitor control devices had an average incidence rate of 31.5 complications per 1000 patient days. To show noninferiority of the Pristine™ Catheter, a 5 complications per 1000 patient days non-inferiority margin is used to establish a performance goal (PG) of 36.5 events per 1000 patient days.

The Primary Patency endpoint will be evaluated by the following hypothesis:

$H_0$ : The complication rate through 3 month is greater than or equal to 36.5 events per 1000 patients days at 3 months.

$H_1$ : The complication rate through 3 month is less than 36.5 events per 1000 patient days at 3 months.

That is:

$H_0: \lambda \geq \lambda_0$

$H_1: \lambda < \lambda_0$

Where  $\lambda_0$  is the PG of 36.5 events per 1000 patient days.

A one-sided p-value will be derived based on a Poisson distribution. The Pristine™ Catheter will be considered to have achieved the primary endpoint objective if the one-sided p-value is less than 0.025.

Conditioned on the success of the above test, a superiority test will be conducted to show that the Pristine™ Catheter is superior to the performance goal. The above test will be repeated with a PG of 26.5 events per 1000 patient days.

The analyses of the primary endpoint will be based on the mITT population and repeated with per-protocol population as sensitivity analyses. The analyses will be conducted after the last active treated subject completes their 3-month follow-up. The number of complications per 1000 patient days will be estimated by Poisson regression model with only the intercept term, and the estimate and 95% CI will be provided using the Wald method, and the p-value comparing to the PG will be calculated by a Chi-square test.

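### Protocol 4.2 misstates the primary performance goal as 31.5 per 1000 catheter days; the operative test uses 36.5 per 1000 patient days

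*Protocol*

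**What the plan says.** Protocol 4.2, the design rationale, states: "The combined safety and performance primary endpoint is compared to a performance goal of 31.5 complications per 1000 catheter days". It mentions neither 36.5, nor the margin of 5, nor a two-step test. The same section ends by saying that a significant difference against the performance goal will attest to the catheter's performance, safety and clinical benefit.

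Protocol 10.5 gives 31.5 a different role: "competitor control devices had an average incidence rate of 31.5 complications per 1000 patient days". The margin of 5 "is used to establish a performance goal (PG) of 36.5 events per 1000 patient days", and the null hypothesis is a rate at or above 36.5. If that null is rejected, "The above test will be repeated with a PG of 31.5 events per 1000 patient days". The synopsis says the same. SAP 2.8 and 5.2.2 also set primary success at 36.5 per 1000 patient days with one-sided p below 0.025. For the superiority step, however, SAP 5.2.2 says: "The above test will be repeated with a PG of 26.5 events per 1000 patient days".

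Protocol 10.2 uses one label for two numbers. One bullet reads "The complication rate of our performance goal is estimated at 31.5 events per 1000 patient days", and the next sets the performance goal at 36.5. Its stated objective is to "show the overall complication rate for Pristine is non-inferior to the performance goal at 3 months". SAP 2.4 repeats this text.

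SAP 5.2.1 is the only place that defines exposure. It ends at removal for transplant, AVG/AVF, peritoneal dialysis, withdrawal of care or other reasons, at early discontinuation, or at the 3-month visit (day 105 at the latest).

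**The concern.** A reader who takes the definition from 4.2 will understand a met performance goal to mean a complication rate significantly below the DOPPS rate. The primary test supports only a rate significantly below the DOPPS rate plus 5. Protocol 3 says the results are intended for the device's labeling, so the phrase needs one meaning.

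The label is also loose within the statistical sections. The 36.5 already contains the margin, so calling the device non-inferior to the performance goal can be read as applying the margin a second time.

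The unit shifts together with the number: catheter days in 4.2, patient days (sometimes just days) elsewhere. The two differ whenever days without the catheter stay in the denominator. In that case the observed rate falls for a reason unrelated to the device.

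**Working it through.** **1. Which threshold is the trial powered on?** Inputs from Protocol 10.2: null 36.5, true rate 31.5 per 1000 days, one-sided alpha 0.025, Type 2 error 0.2, attrition 15%, stated exposure 12,765 days, 142 participants at 90 days.

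- Exact one-sample Poisson test at 10,850 days: expected events under the null are 0.0365 × 10,850 = 396.0. The largest count with a lower-tail probability below 0.025 is 357 (tail probability 0.02499). Power at a true rate of 31.5 is 80.3%.
- Inflating for attrition: 10,850 / 0.85 = 12,765 days, and 12,765 / 90 = 141.8, so 142.
- Superiority, null 31.5 and true rate 26.5, at 10,850 days: the critical count is 305 and power is 85.5%, against the stated 85%.
- Cross-check by normal approximation: [(1.960√0.0365 + 0.842√0.0315) / 0.005]² = 10,976 days, and 10,976 / 0.85 ≈ 12,913, about 1% above the stated figure.

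The plan's figures reproduce with 36.5 as the primary null and 31.5 as the superiority null.

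**2. How far apart are the two readings?** Largest count, and largest observed rate, that gives one-sided p < 0.025 (exact Poisson):

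| Exposure (days) | Against 36.5 | Against 31.5 |
|---|---|---|
| 12,765 | 423 events (33.1 per 1000) | 362 events (28.4 per 1000) |
| 10,850 | 357 events (32.9 per 1000) | 305 events (28.1 per 1000) |

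An observed rate above about 28 and up to about 33 meets the goal in 10.5 but not the goal as worded in 4.2.

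**3. The superiority goal in SAP 5.2.2.** SAP 2.4 and Protocol 10.2 give 26.5 as the assumed Pristine rate and 31.5 as the superiority goal. With 26.5 as the null, the critical count is 254 at 10,850 days and 302 at 12,765 days. At a true rate of 26.5 the chance of success is 2.4% in both cases, against the stated 85%.

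**4. The denominator.** SAP 5.3.5 shows that infection and catheter dysfunction are removal reasons of their own on the re-intervention form. SAP 5.2.1 omits them from the reasons that stop exposure. Unless such a removal is also recorded as discontinuation, the days after it continue to count, up to the 3-month visit or day 105. For scale only, on an assumed range that is not in the documents: if catheter days were 80% to 95% of patient days, 31.5 per 1000 catheter days would equal 31.5 × 0.80 = 25.2 to 31.5 × 0.95 = 29.9 per 1000 patient days.

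**The case against.** The strongest reply is that nobody running the analysis could be misled. Every formal hypothesis uses 36.5, the sample size is built on it, and 4.2 contains no hypothesis, alpha or decision rule. The bullets in 10.2 derive 36.5 from 31.5 in plain sight, and an observed rate between about 28 and 33 is simply the planned outcome of non-inferior but not superior. This stands. A reader might infer from 4.2 that the protocol holds two competing primary criteria, and the documents do not support that. Nor should one say that the trial has only about a 2.3% chance of success under 4.2: testing 31.5 when the true rate is 31.5 returns roughly alpha by construction, and no section plans 31.5 as the first step.

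On the unit, Protocol 7.5 keeps participants in the study until completion or the day of catheter removal. If every removal is entered as a discontinuation, the second stopping rule in SAP 5.2.1 closes the gap. That is a fair point, but the SAP does not say that removal is handled this way, and its separate list of removal reasons would then be unnecessary.

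A reader might also conclude that the benchmark and the observed rate are not comparable. The documents do not show this: the same 31.5 appears per catheter day in 4.2 and per patient day elsewhere, and the source cannot be checked here.

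**Conclusion.** Section 4.2 is wrong about the primary threshold and out of step on the unit. The decision rule for the primary test is 36.5 and is not in doubt. The consequence is one of interpretation: the required observed rate differs by about 4.8 per 1000 (33.1 against 28.4 at 12,765 days; 32.9 against 28.1 at 10,850 days), and the closing claim of 4.2 attaches clinical benefit to the stricter reading. These figures assume Poisson counts, as the plan does.

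Two related points go beyond wording. The superiority goal differs between protocol (31.5) and SAP 5.2.2 (26.5), and the SAP value would leave that step with about 2.4% power at the rate assumed for it. The exposure rule in SAP 5.2.1 can admit days without the catheter and so lower the rate. How much depends on how often catheters are removed for infection or dysfunction and on how such removals are recorded, neither of which the documents give. The corrections should be made before the 3-month analysis.

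**What to change.** 1. In Protocol 4.2, 10.2 and the synopsis, and in SAP 2.4, call 31.5 the DOPPS benchmark and 36.5 the primary performance goal. State that 31.5 serves as a test threshold only in the conditional superiority step. Where the objective speaks of non-inferiority to the performance goal, say instead that the rate is below it.
2. In SAP 5.2.2, change the superiority goal from 26.5 to the 31.5 in Protocol 10.5.
3. In SAP 5.2.1, end exposure at catheter removal for any reason, including infection and catheter dysfunction. Use that one unit in every section that states a rate, and confirm from the cited source that the DOPPS 31.5 is expressed in the same unit.

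Items 1 and 2 are text edits. Item 3 needs a small change to the derived-data programming and gives slightly less exposure, hence slightly less power.
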